3.2.2 Referrals from primary care

Clinics can refer patients into the local hunger safety net through standard food bank protocols. Enrollment into the study for these participants will proceed through the standard process outlined in the MOP. We cannot accept referral of clinic patients directly into the study.

3.2.3 Communication with health care provider

Communication with the health care provider will be informed by the Health Care Utilization Analysis Plan (see **section 7.7**).

3.3 Diabetes-appropriate food boxes

Through the 6-month intervention, FAITH-DM participants will receive 11 bi-monthly food packages (twice monthly). The main goal of the food packages will be to increase participants' access to foods appropriate for diabetes self-management. The food packages will aim to provide approximately 25% of a participant's food needs for the month, equating to about 11 meals from each food package. Additionally, the food packages will serve as a model for healthy food choices for people living with diabetes.

Food group servings for the baseline food package will include a box with non-perishable items (canned, boxed, or other shelf-stable vegetables, fruits, grains, meats, beans, etc.), as well as supplemental perishable items (e.g. fresh vegetables and fruits, bread, dairy, meat, poultry) in a bag intended to serve a household of 1-2 people. In order to address varying household sizes, guidelines for distribution of food packages will be as follows:

Household Size (# persons)	Food Package Guidelines
1 - 2	1 standard box of non-perishables and 1 standard bag of perishables
3 - 4	1 standard box of non-perishables and 2 standard bags of perishables
5 or more	2 standard boxes of non-perishables and 2 standard bags of perishables

Food Box Criteria:

Based on USDA guidelines for number of servings of different food groups for an adult male

- Sufficient food items and variety to create 11 meals
- Focus on vegetables and fruits, whole grains, low-fat dairy, lean meat
- Ideal breakdown of food package by servings
 - 30- 40% non-starchy vegetables
 - 10 - 20% fruit
 - 25% grains and other carbohydrates (includes corn and potatoes)
 - 25% lean protein and dairy

Food Group	What equals a choice?	Number of choices per food package

Vegetables - non-starchy vegetables including a variety of types. Canned should be low-sodium or “no salt added”.
	
Fresh vegetables: 1 head, 1 bunch or 1 pound = 1 choice Canned vegetables (no salt added), 15 oz = 1 choice Spaghetti sauce, 15 oz = 1 choice Frozen Vegetables, 16 oz = 1 choice
	
9 (Ideally 4-5 fresh/perishable and 4-5 shelf-stable)

Fruits - include a variety of fruits. Canned should be no-sugar added or packed in 100% juice. No fruit juice.
	
Fresh fruit: 1 bunch, 1 pound, or 4 pieces = 1 choice Frozen Fruit, 12 - 16 oz = 1 choice Canned Fruit, 15 oz = 1 choice
	
3 (Ideally 2 perishable and 1 shelf-stable)


Proteins - Meat & Non-Meat - Focus on lean meats
	
Canned Beans, 15 oz = 1 choice Dried beans, 1 pound = 1 choice Peanut Butter, 18 oz = 2 choices Dozen eggs = 1 choice Frozen meat, fish, poultry, 1 lb = 2 choices Canned chicken, tuna, salmon, 5 oz, 1 can = 1 choice Tofu, 14 oz package = 1 choice
	
6 Ideally 2-3 perishable and 3-4 shelf-stable

Dairy - Low fat dairy
	
1/2 gallon milk, 1% or skim = 1 choice Shelf Stable milk, 1% or skim quart = 1 choice 4 yogurts, 6 oz each = 1 choice Cottage Cheese, 8 oz = 1 choice Mozzarella, Cheddar, Swiss cheese, 8 oz = 1 choice
	
2

Grains and other starches - at least 50% whole grains; ready-to-eat cereal < 8g sugar and 3g fiber per serving
	
Whole grain bread, 1 loaf = 1 choice 6 rolls or bagels = 1 choice Package Tortillas, whole grain = 1 choice Brown Rice, 1 bag, 16 oz = 1 choice Pasta, 16 oz = 1 choice Oatmeal, 18 oz = 1 choice Ready to Eat Cereal, 12 - 16 oz = 1 choice Corn, 15 oz = 1 choice Potatoes, yams, 1lb bag = 1 choice
	
5 2 perishable and 3 shelf-stable

Other
	
Coffee, tea, spices, low-sodium condiments, non-stick pan spray, salad dressing Olive oil and/or canola oil to be given out 2 times during the intervention
	
1-2 items

Example Food Package

Box

Diced tomatoes, no salt added (2-15.5 oz. cans)
Peas, no salt added (1-15.5 oz. can)
Green Beans, no salt added (1-15.5 oz. can)
Mixed vegetables, no salt added (1-15.5 oz. can)
Applesauce, no sugar added (1-15.5 oz. can)
Black beans (1-15.5 oz. can)
Pinto beans (dry, 1 lb.)
Salmon (1-14.75 oz. can)
Peanut Butter (1-18 oz. jar)
Box pasta, whole wheat (dry, 1 lb)
Bag Brown Rice (dry, 1 lb)
Box of high fiber cereal (dry, 18 oz.)
Olive Oil

Italian Seasoning

Perishables

Salad mix (10 oz.)
Broccoli (1-2 heads)
Carrots (1 lb.)
Snap peas (1 lb.)
Oranges (1 lb.)
Grapes (1 lb.)
Chicken thighs, frozen (1 lb.)
Eggs (1 dozen)
Milk, 1% or skim (1/2 gal.)
Cheddar cheese (8 oz.)
Bread, whole grain (1 loaf)
Tortillas, whole grain (1 pkg.)

3.4 Diabetes self-management education (DSME) and support (SMS)

A major component of the intervention is to provide study participants with diabetes self-management education and support that is culturally appropriate and tailored to meet their needs relative to their socio-economic status, literacy level, and food security challenges. We have drawn from evidence-based practice and adapted existing diabetes education curricula to develop a structured intervention that is designed to be flexible to accommodate individual, community, and site variations.

The FAITH-DM educational intervention is modeled on the American Association of Diabetes Educators “AADE7™ Self-Care Behaviors”. These seven self-care behaviors include:

- Healthy Eating
- Being Active
- Monitoring
- Taking Medications
- Problem-Solving
- Healthy Coping
- Risk-Reduction

The FAITH-DM curriculum was primarily adapted from the “Type 2 Diabetes BASICS” curriculum (Park Nicollet International Diabetes Center), with additional content adapted from educational materials used in the “Improving Diabetes Care and Outcomes on the South Side of Chicago” project (Peek M., Chin M., University of Chicago). The FAITH-DM curriculum addresses the AADE7™ through a combination of group classes, 11 packets of written education materials to accompany the

food box distributions, and one-on-one interactions to reinforce those messages. A “Train the Trainer” model will be used to build capacity among the health educators at each site who will be implementing the intervention with study participants.

The three DSME components of the education and support intervention described below include:

- Formal DSME Group Classes (2 sessions with monthly drop-in sessions): **section 3.4.1**
- Brief one-on-one interactions to reinforce DSME messages: **section 3.4.2**
- Passive education materials (11 bi-monthly packets of written educational materials to accompany the food box distributions): **section 3.4.3**

*** **Note:** Intervention group and control group participants **receive different elements** of the study DSME program (see below). Food bank education staff will need to maintain a process to ensure participants receive the correct educational components based on their group assignment (the study MS Access database will support this process). This group difference will allow us to assess the effectiveness of DSME components at the study’s end.

All outreach and communication related to diabetes programming for participants in the intervention group should be **targeted to the individual** (using project reminder cards for group classes, phone calls, 1-on-1 in-person meetings, etc.). Food bank education staff should **NOT** use global outreach strategies (general announcements, flyers, posters, mass mailings, etc.) to promote any diabetes education components to the general food bank population.

Overview of DSME Components by Participant Group		
DSME Component	Intervention Group	Wait List Control Group
Group Classes (includes monthly drop-in sessions)	Yes	No
1-on-1 Interactions	Yes	Yes, after waiting period
ACP “Living with Diabetes” Guide	Yes, at enrollment	Yes, after waiting period
Bi-monthly passive education materials with food packages	Yes	Yes, after waiting period

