To help maximize attendance at Sessions 1 and 2, sites will offer supplies to participants in attendance to support their diabetes self-management. Supplies will include items such as water bottles, measuring cups, re-usable grocery bags, cookbooks, medication pill boxes, foot mirrors, pedometers, and stress balls. Grant awards include funding for these items.

Group classes (including the monthly drop-in sessions) are only offered to participants randomized to the intervention group.

Group Classes

Group classes will be offered twice each month (or as needed) at varied days, times, and locations to maximize attendance. Classes will be conducted in English and Spanish by trained health educators. Each class session lasts 2 – 2.5 hours, and a class series will include 2 sessions with follow-up drop-in sessions for ongoing support. Class structure will emphasize participant involvement, group discussion and interaction, participant teachback, use of visual aids, and repetition of clear, simple messaging around key self-management strategies.

Class sessions will be scheduled so that all study participants can complete session 1 within 1 month of their enrollment date, and session 2 within 2 months of their enrollment date.

Session 1: Introduction to Diabetes – provide participants with basic information needed for diabetes self-management including disease overview, healthy eating strategies, physical activity, blood sugar monitoring, and treatment plans. Primary AADE7™ behaviors addressed: Healthy Eating, Physical Activity, and Monitoring.

Session 2: This session will focus on living with diabetes given the challenges of food insecurity and other common issues for food pantry clients. Primary AADE7™ behaviors addressed: Problem Solving, Healthy Coping, and Risk Reduction.

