3.6 Length and time windows for intervention

For participants in the intervention group, access to the food package and DSME intervention components is only available during their 6-month intervention window (T0-T6). Intervention group participants should no longer have access to these elements after they reach their T6 time point in the study (they will have access to referrals for care, if needed, at T6 and T12, and have access to HbA1c testing and monitoring at T6 and again at T12).

For participants in the control group, access to the food package and the modified DSME intervention components is also only available during their 6-month intervention window (T6-T12). Control group participants should not have access to intervention components prior to T6, nor should they continue receiving any intervention components after T12. Control group participants will have access to referrals for care, if needed, at T6 and T12, and have access to HbA1c testing and monitoring at T6, T9, and again at T12 per existing study protocols.

Site adherence to these time windows will help achieve and maintain fidelity to the original study design. While sites may need to make minor, reasonable accommodations for individual participants (e.g., provision of a maximum of 2 food packages to be picked up within 1 month post T6 follow-up activities for intervention group participants), any deviation from these protocols should be logged in the MS Access database for the participant, and site staff should complete and submit a Protocol Deviation (**Appendix F**) form.

Any food bank services (e.g., food packages, education, support, referrals) provided or conducted after T12 activities for any study participant will be at the discretion of the food bank as these clients will no longer be enrolled in the study as active study participants.

4 Recruitment and Retention Plan

In order to meet recruitment targets, we will:

- Monitor recruitment and intervene quickly to change recruitment techniques that are proving unsuccessful; discuss on monthly calls
- Identify barriers to recruitment
- Use multiple recruitment strategies depending on the needs of each food bank or food pantry (see **Appendix AJ** for a sample recruitment flyer to post at pantry sites)
- If we are not meeting recruitment goals, we can employ additional outreach strategies such as English and Spanish language flyers and advertisements

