7.7.8 Provider Packet Summary Table

The table below summarizes the different types of provider packets to be assembled at baseline and follow-up based upon the participant’s enrollment in the intervention or control group and their reporting of a PCP:

	Intervention group	Control group
Existing PCP	
At T0: HCU Letter 1 - T0 Current Pt INT, signed forms, information sheets
 
At T6: HCUS, HCU Letter 4 - T6 Current Pt, signed forms
 
At T12: HCUS, HCU Letter 7 – T12 Current Pt, signed forms
	
At T0: HCU Letter 3 - T0 Current Pt CONT, signed forms, information sheets
 
At T6: HCUS, HCU Letter 4 - T6 Current Pt, signed forms
 
At T12: No provider communication

No existing PCP (at T0)	
At T0: HCU Letter 2 - T0 Newly Referred Pt INT, signed forms, information sheets
 
At T6: HCUS, HCU Letter 4 - T6 Current Pt, signed forms
 
At T6: If participant still doesn't have PCP: HCU Letter 5 - T6 Newly Referred Pt, HCUS, signed forms, information sheets
	
At T0: No provider communication, but participant will be encouraged to see PCP
 
At T6: If participant now has PCP: HCUS, HCU Letter 4 - T6 Current Pt, signed forms, information sheets
 
At T6: If participant still doesn't have PCP: HCU Letter 5 - T6 Newly Referred Pt, HCUS, signed forms, information sheets

	
At T12: HCUS, HCU Letter 7 – T12 Current Pt, signed forms
 
At T12: If participant still doesn't have PCP: HCU Letter 8 – T12 Newly Referred Pt, HCUS, signed forms, information sheets
	
At T12: If participant now has a PCP, no provider communication
 
At T12: If participant still doesn't have PCP, use "Screening and Referral Form" to complete active referral

--	---	--

8 Randomization

In randomized, controlled clinical trials, participants are assigned to a treatment group based upon a pre-determined randomization scheme developed by the study statistician ([name], UCSF). Randomization is used to reduce bias in assignment to treatment. In our case, clients will be randomized to receive the intervention immediately or after a 6-month delay.

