- Month 5, Week 2
 - Participant receives bi-monthly food box, passive education materials, and 1-on-1 education from food bank staff
- Month 6, Week 1 = T6
 - Participant completes 6-month HbA1c test with study staff
 - Participant completes T6 survey with study staff (CASIC)
 - Participant receives \$30 gift card for completion of survey
 - Participant receives final bi-monthly food box, passive education materials, and 1-on-1 education from food bank staff
 - Participant attends monthly group drop-in diabetes education class
- Month 12 = T12

- Participant completes 12-month HbA1c test with study staff
- Participant completes T12 INT survey with study staff (CASIC)
- Participant receives \$15 gift card for completion of survey
- Participant formally exits research study

Participants – Control Group

- Day 1 (Month 1, Week 1) = T0
 - Food bank client participates in diabetes screening (blood glucose and/or HbA1c testing) event at food pantry; study staff verifies that client meets eligibility requirements for study inclusion
 - Client agrees to participate in study and completes written consent form with study staff
 - Participant completes baseline survey with study staff (CASIC)
 - Participant randomly assigned to study control group by study staff
 - Participant receives \$15 gift card for survey completion
- Month 1, Week 1 – Month 6, Week 2
 - Participant attends regular food pantry distributions and receives normal services per food pantry guidelines (does NOT receive diabetes food packages or education)
- Month 7, Week 1 = T6
 - Participant completes HbA1c test with study staff
 - Participant completes final survey with study staff (CASIC)
 - Participant receives \$15 gift card for survey completion
 - Participant receives 1st bi-monthly food box, passive education materials, and 1-on-1 education from food bank staff
- Month 7, Week 2
 - Participant receives bi-monthly food box, passive education materials, and 1-on-1 education from food bank staff
- Month 8, Week 1
 - Participant receives bi-monthly food box, passive education materials, and 1-on-1 education from food bank staff
- Month 8, Week 2
 - Participant receives bi-monthly food box, passive education materials, and 1-on-1 education from food bank staff
- Month 9, Week 1
 - Participant receives bi-monthly food box, passive education materials, and 1-on-1 education from food bank staff
- Month 9, Week 2 = T9

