17.3.1 Extension plan

In late 2015, the Urban Institute was awarded a grant from the Robert Wood Johnson Foundation (RWJF). Under the grant, Urban will serve as a transdisciplinary research hub in support of RWJF's *Policies for Action: Policy and Law Research to Build a Culture of Health*. Urban has dedicated a part of this award is towards ancillary, or "extension", funding for FAITH-DM.

As initially outlined in **section 17.3** (Ancillary Funding), this extension funding will be dedicated towards additional HbA1c testing, survey administration, and HCU activities for participants at the 12-month (T12) mark. An overview of these activities is provided here:

T12 Activity	Intervention Group	Control Group
HbA1C Testing	Yes – new extension activity	Yes – original protocol
Participant T12 Post-Survey	Yes – new extension activity	Yes – revised from original protocol
HCUS Provider Survey	Yes – new extension activity	No

Primary rationale for extension activities:

- The T12 follow-up activities with the intervention group will provide important data on how well participants **maintain** any benefits that they may have experienced at the immediate end (T6) of the intervention. Identifying health promotion interventions that positively impact outcomes for the long term has important implications for public health programming and policy development.
- The extension plan will also allow us to compare, to a degree, the efficacy of the primary study intervention to the “modified” intervention that the control group receives. This comparison may provide important information on how well specific intervention components work (e.g., the formal vs. modified DSME program).

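### The design has no concurrent randomized comparison of full versus modified DSME, so the group difference cannot show which education components work

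*Combined protocol and SAP*

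**What the plan says.** Section 3.4, in a note on the education elements each group receives, states: "This group difference will allow us to assess the effectiveness of DSME components". It adds no limit, model or estimand.

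Section 17.3.1 gives as a reason for the T12 extension that it will let the team "compare, to a degree, the efficacy of the primary study intervention" with the modified version the control group receives. It continues: "This comparison may provide important information on how well specific intervention components work", naming formal versus modified DSME as the example.

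The design facts that bear on this are as follows.

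- Section 8 (Randomization): "clients will be randomized to receive the intervention immediately or after a 6-month delay". Timing is what is randomized, and the education program goes with it.
- Section 3.6: the intervention arm has food packages and DSME in T0-T6 only. The control arm has food packages and modified DSME in T6-T12 only.
- Section 3.4.1: "Group classes (including the monthly drop-in sessions) are only offered to participants randomized to the intervention group". The overview table in Section 3.4 shows that 1-on-1 contacts, the diabetes guide and the written packets reach both arms, the control arm after its wait.
- Section 9.1: while waiting, controls receive ordinary pantry services, without the diabetes food packages or education.
- Sections 13.4.3 and 13.4.4: the powered hypothesis is HbA1c over six months, and the model is an ANCOVA on assigned arm and baseline value. No full-versus-modified analysis is specified. The one component-level analysis is by engagement, and there the plan concedes that the benefits of randomization are lost.

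**The concern.** To learn whether group classes add anything, one would compare participants given the full program with participants given the modified program over the same period, with assignment at random. Here the two programs are never delivered in the same period. A reader of Section 3.4 would nevertheless expect the trial to yield evidence on the components.

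What is at stake is a secondary conclusion about group classes, with obvious use for programme planning. The natural way to draw it from these data, setting the change in each arm's treated window side by side, tends to favour the full program even if classes do nothing.

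**Working it through.** **The possible comparisons**

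| Comparison | Intervention arm | Control arm | What it tests |
|---|---|---|---|
| Between arms at T6 | Just finished the full package | Waited, no package | Randomized and concurrent: whole package versus waiting |
| Between arms at T12 | Off treatment about six months | Just finished the modified program | Randomized: full-then-off versus wait-then-modified |
| Treated window against treated window | T0-T6 change | T6-T12 change | Non-concurrent; not protected by randomization |

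None isolates DSME content. At T6, food boxes, DSME, active referral and the extra HbA1c test vary together. At T12, classes are aliased with delivery time and time since treatment. In the third comparison, the intervention window opens at the reading that qualified the person (7.5% or more, Section 5.2). The control window opens six months later, without a new threshold and only in those still followed (20% attrition is allowed for in 13.4.1).

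Even without this aliasing, only classes plus drop-in sessions, as one block, differ between the two DSME programs.

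**Reproducing the plan's figure**

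Inputs from 13.4.1: difference 0.4, SDs 1.6 and 1.9, r = 0.51, two-sided 5%, 90% power.

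n per arm = (1.960 + 1.282)² × (1.6² + 1.9²) × (1 − 0.51²) / 0.4² = 299.8, so 300, as stated. This covers the T6 comparison of HbA1c; no power statement exists for DSME components.

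**Size of regression to the mean in the T0-T6 window (illustrative)**

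Expected fall = (1 − b) × (9.5 − m). The 9.5% is the projected starting mean in 13.4.1. The usual mean m and the slope b of follow-up on baseline are not in the documents, so both are assumed. The slope equals r = 0.51 if the SDs at the two times are equal. If 1.6 and 1.9 are pre and post SDs (also an assumption), b = 0.51 × 1.9/1.6 = 0.61.

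| m | b = 0.51 | b = 0.61 | b = 0.7 | b = 0.9 |
|---|---|---|---|---|
| 9.0% | 0.25 | 0.20 | 0.15 | 0.05 |
| 8.5% | 0.49 | 0.39 | 0.30 | 0.10 |
| 8.0% | 0.74 | 0.59 | 0.45 | 0.15 |
| 7.5% | 0.98 | 0.79 | 0.60 | 0.20 |

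The range is 0.05 to 0.98 points. Against the 0.4-point target, that is 0.05/0.4 = 12.5% to 0.98/0.4 = 245%.

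These figures are the fall in T0-T6 alone. If regression continued at the same slope, the control arm's T6-T12 window would hold a further b × (1 − b) × (9.5 − m), and the difference between windows would be (1 − b)² × (9.5 − m). With m = 8.5 and b = 0.51 that is 0.49² = 0.24 instead of 0.49. The direction is the same and the size smaller.

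**The case against.** Five points can be made for the plan.

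- **Section 17.3.1 already hedges.** It does, but it names neither the timing nor the time-since-treatment problem, and it keeps the component use. Section 3.4 has no hedge.
- **The arms at T12 are randomized.** This stands. A reader might infer that the T12 between-arm contrast is non-randomized, and the documents do not support that. Section 8 randomizes people to immediate or delayed intervention, so T12 validly compares two sequences. What it cannot do is attribute a difference to DSME content.
- **Regression to the mean belongs to an analysis the plan does not specify.** This also stands. No section proposes comparing raw changes across treated windows. If the ANCOVA of 13.4.4 were used at T12, both arms would share the same T0 selection, and regression to the mean would be expected to be equal. The bias is a risk in the comparison a reader would need for a full-versus-modified reading; it is not a flaw in a planned model.
- **The size is uncertain.** Agreed. A reader might infer a bias as large as the planned effect or larger. That depends on a usual mean the documents do not give, on taking r as the slope, and on little further regression after T6.
- **The sentence in 3.4 is a note to education staff, and no primary or secondary result rests on it.** True, which limits the consequence. It still states a property that the design lacks, and 17.3.1 carries the same use into the rationale for the extension.

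**Conclusion.** The claim in Section 3.4 is not supported by the design, and the hedge in 17.3.1 does not repair it. This follows from the schedule alone and needs no numerical assumption: full and modified DSME are never given concurrently to randomized groups, and most DSME elements reach both arms.

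The size of bias in a treated-window comparison is illustrative only: 0.05 to 0.98 HbA1c points for m of 7.5 to 9.0% and b of 0.51 to 0.9, less if regression continues beyond T6. Its expected direction favours the full program.

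A reader might go further and doubt the main result. The documents give no ground for that here: the T6 comparison is concurrent, randomized and adjusted for baseline, and this point leaves it untouched.

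**What to change.** **Section 3.4.** Delete the sentence, or replace it with a statement that the full-versus-modified DSME comparison is exploratory and confounded with timing.

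**Section 17.3.1.** State that:

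- the T12 between-arm contrast is a randomized comparison of an immediate-full with a delayed-modified sequence, and does not isolate DSME components;
- any comparison across treated windows is exploratory and non-concurrent, and supports no causal conclusion about components.

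**If window changes are reported.** Give the intervention arm's T0-T6 change net of the control arm's T0-T6 change. Beside it, state that the control arm's T6-T12 change has no concurrent untreated control.

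**Cost.** Wording only. No visit, measurement or sample size changes. The trial gives up a secondary claim it cannot support.
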